#### Visual analogue scale – Bowdle

Descriptive statistics of the 13 individual Bowdle scales at screening and post examination and for the difference from baseline (=screening) will be provided. Other assessments will be listed only.

Furthermore, for the SRD part, the change from baseline of the individual scales will be presented graphically over time (arithmetic means + standard deviation).

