5.2.5.3 Visual Analogue Scale (VAS)

Possible psychedelic effects will be monitored and evaluated as safety measurement by analogue scales developed by Bond and Lader [[R98-0752](#)] and Bowdle along with PK sampling. From these measurements, following factors are derived - external and internal perception, alertness, mood and calmness.

The VAS assessments 2 hours before drug administration will be considered as baseline. At each measuring time point indicated in the [Flow Chart](#), the subjects will assess their subjective impression by themselves by means of a visual analogue scales. The subjects will be asked to mark an adequate position on a line between the two limits characteristics. The length of the line will be exactly 100 mm, and will ascertain a score number (values between

0 and 100) by measuring the distance in mm from the beginning of the line to the position marked by the subject. The score will be documented in the electronic case report form.

The original English version is shown in [Appendix 10.1](#).

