## **6.7 BASELINE, TIME WINDOWS AND CALCULATED VISITS**

For the analysis of vital signs and VAS the baseline value is defined as the last measurement before trial drug administration (SRD part) / before trial drug administration in each treatment period (FE part).

For laboratory analysis the baseline is defined as the last measurement before trial drug administration in the first period.

**Section 6.1 of the CTP:** *Exact times of measurements outside the permitted time windows will be documented. The acceptable time windows for screening and end of trial examination are given in the CTP Flow Chart.*

*Study measurements and assessments scheduled to occur 'before' trial medication administration on Day 1 are to be performed and completed within a 2 h-period prior to the trial drug administration (including blank values for PK and biomarkers).*

*The acceptable deviation from the scheduled time for vital signs, orthostatic testing and ECG will be  $\pm 10$  min and laboratory tests will be  $\pm 30$  min for the first 4 h after trial drug administration and  $\pm 30$  min thereafter.*

[...] *The acceptable deviation from the scheduled time for standardized neurological tests (conducted in Dose Group 200 mg fed) is  $\pm 45$  min on day 1, and  $\pm 90$  min from day 2 onwards.*

Adherence to time windows will be checked via the consistency check listings at the RPM/DBLM.

**Section 5.2.4 of the CTP:** *With the exception of the first triple ECG (used as baseline before the first drug administration), only the first of the three replicate ECGs at a single assessment time will be evaluated.*

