### 7.8.5.3 Visual Analogue Scale (VAS) - Bond & Lader and Bowdle

The VAS will be used at screening and at end of trial examination, as well as on predose at visit 3 (FE part only) and planned times -1:00 (dose groups 3mg to 50mg), -0:30 (dose groups 100mg, 200mg and 200mg fed), 2:00, 4:00, 8:00, 24:00, 34:00 and 48:00 (SRD part only).

The last VAS assessments before drug administration will be considered as baseline.

The results of both VAS will be listed and descriptive statistics over time including change from baseline will be performed.

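### SAP 7.8.5.3 gives the Bowdle scale a screening baseline and a two-time table, against the pre-dose baseline and over-time summaries stated elsewhere in the SAP

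*SAP*

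**What the plan says.** SAP 7.8.5.3 opens with a lead-in under a heading that names both Bond & Lader and Bowdle. On baseline it says: "The last VAS assessments before drug administration will be considered as baseline". On output it says: "The results of both VAS will be listed and descriptive statistics over time including change from baseline will be performed". It schedules the VAS at screening and end of trial in both parts, and before dosing at visit 3 in the FE part. In the SRD part it adds the following times (the first carries a minus sign): "1:00 (dose groups 3mg to 50mg), -0:30 (dose groups 100mg, 200mg and 200mg fed), 2:00, 4:00, 8:00, 24:00, 34:00 and 48:00".

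SAP 6.7 gives the same baseline rule: "For the analysis of vital signs and VAS the baseline value is defined as the last measurement before trial drug administration". For the FE part it applies that rule within each treatment period.

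The Bowdle paragraph of SAP 7.8.5.3 says something different: "Descriptive statistics of the 13 individual Bowdle scales at screening and post examination and for the difference from baseline (=screening) will be provided". It continues: "Other assessments will be listed only". Its next sentence requires, for the SRD part, that "the change from baseline of the individual scales will be presented graphically over time (arithmetic means + standard deviation").

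Protocol 5.2.5.3, which introduces both scales, also uses a pre-dose baseline: "The VAS assessments 2 hours before drug administration will be considered as baseline". SAP section 4 declares one departure from the protocol, the move from 95% to 90% confidence intervals. It mentions no change to the VAS baseline.

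**The concern.** A programmer working on the SRD part meets two baselines for the same scale and two accounts of which times are summarised, with no statement of which governs. Two people following this SAP could deliver different Bowdle tables.

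The choice has consequences. Protocol 5.2.5.3 uses these scales to monitor possible psychedelic effects as a safety measurement, alongside PK sampling. If the Bowdle paragraph governs, the only tabulated change compares end of trial with screening. End of trial is planned for Day 10 to 14, or Day 29 to 33 in the 200 mg fed group. The hours after a single dose, when an acute effect would be expected, drop out of the tables.

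**Working it through.** No power or sample-size figure is involved. The check sets the texts side by side and counts planned times, using the schedule in SAP 7.8.5.3. I read post examination in the Bowdle paragraph as end of trial.

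**Baseline, SRD part**

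| Source | Bowdle baseline |
|---|---|
| SAP 7.8.5.3, Bowdle paragraph | screening |
| SAP 7.8.5.3, lead-in for both scales | last value before dosing |
| SAP 6.7 | last value before dosing |
| Protocol 5.2.5.3 | pre-dose, 2 hours before |

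- The protocol's 2 hours fits the pre-dose window in footnote 2 of the SRD Flow Chart, under which such procedures are completed within 2 h before dosing. I therefore do not count it as a third rule. On any reading it is not screening.
- Screening would satisfy the lead-in only if no later pre-dose VAS existed. One is scheduled in every SRD group: at -1:00 in 5 groups (3, 6, 10, 25, 50 mg) and at -0:30 in 3 groups (100, 200, 200 mg fed); 5 + 3 = 8 of 8.
- Screening is Day -21 to -1 and dosing is Day 1. With no Day 0, the screening baseline is 1 to 21 days before dosing, against a nominal 1 h or 0.5 h.

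**Times, SRD part**

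- Planned: 1 screening + 1 pre-dose + 6 post-dose (2, 4, 8, 24, 34, 48 h) + 1 end of trial = 9.
- Tabulated under the Bowdle paragraph: screening and end of trial = 2 of 9. Not tabulated: 9 - 2 = 7, namely the pre-dose value and all six post-dose values.
- Change-from-baseline times under the lead-in and SAP 6.7: 6 + 1 = 7. Under the Bowdle paragraph: 1.
- That one change is measured 10 - 1 = 9 to 14 - 1 = 13 days after dosing, or 29 - 1 = 28 to 33 - 1 = 32 days in the 200 mg fed group, on the planned end-of-trial days.

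**The Bowdle paragraph against itself.** It confines the other assessments to listings, then asks for an SRD plot of mean and SD of change over time. That plot needs summary statistics at those same times. It also needs a baseline, which the sentence does not name.

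**Was Bowdle collected only at screening and end of trial?** The texts do not support that. The lead-in's schedule does not separate the two scales. Footnote 15 of the SRD Flow Chart restricts only the suicidality assessment to those two visits.

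**FE part.** There are 3 planned VAS times: screening, visit 3 pre-dose (also in footnote 8 of the FE Flow Chart) and end of trial. The Bowdle paragraph tabulates 2. Screening is the last VAS before the first FE dose, so the rules agree for period 1. For the end-of-trial value they differ: the Bowdle paragraph refers back to screening, and SAP 6.7 refers back to visit 3 pre-dose.

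**The case against.** The best defence is that a scale-specific paragraph overrides a general lead-in. Bond & Lader gets summaries over time in its own paragraph, Bowdle gets a deliberately short table, and the figure supplies the means and SDs over time. On this view the lead-in never promises tables, and the sentence about listings is only loose wording.

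This does not remove the conflict. The lead-in says in terms that it covers both scales. Protocol 7.3.3 says that continuous safety data are analysed by tabulating descriptive statistics, and SAP section 7 defines the summary set for end-of-text tables, so the natural reading of the lead-in is a table. Treating the Bowdle paragraph as a deliberate exception would still leave its figure without a stated baseline and would make the screening baseline an undeclared departure from protocol 5.2.5.3.

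Several points on this side do stand:

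- A short Bowdle table may be what the authors wanted. That bears on which remedy to choose.
- The count of 1 against 7 refers to tabulated changes; the figure would still show the SRD course.
- The counts rest on the SAP's schedule and were not confirmed against the Flow Chart columns, which did not extract cleanly. The 1 h and 0.5 h are nominal times.
- The FE difference is narrow. No FE VAS is planned between dosing and end of trial except the visit 3 pre-dose value.
- The stakes are limited. VAS is not named in the minimum data set for dose-escalation review (protocol 3.1) or in the stopping criteria (protocol 3.3.4.2). The synopsis lists Bowdle as a further safety criterion, but protocol 5.2.1 names only Bond & Lader. Every value is listed under either reading.

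**Conclusion.** The concern holds. In the SRD part the Bowdle paragraph contradicts the section's lead-in and SAP 6.7 on baseline, contradicts the lead-in on which times are summarised, and is at odds with its own figure. Followed literally, it tabulates 2 of 9 planned times and 1 change from baseline instead of 7, measured from a value up to 21 days old. In the FE part the disagreement is confined to the baseline for the end-of-trial change.

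The conclusion assumes that post examination means end of trial and that the SAP's VAS schedule applies to both scales, as its wording indicates. The effect is on descriptive safety output only: neither the primary endpoint nor the PK analyses change. It should be fixed because, as written, the Bowdle table would omit the period in which an acute effect is most likely to show.

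**What to change.** **SRD part.** In the Bowdle paragraph, replace screening as baseline with the last assessment before drug administration, as in SAP 6.7. Summarise the 13 items and their change from baseline at the planned SRD times, by dose group and pooled placebo. Remove the listings-only sentence for this part, and state that the figure uses the same baseline.

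**If a short Bowdle table is intended.** Limit the lead-in's sentence on summaries over time to Bond & Lader and say so. The SRD baseline and the figure's baseline must still be settled. If screening is kept, declare it in SAP section 4 and carve Bowdle out of SAP 6.7.

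**FE part.** State which baseline applies to the visit 3 pre-dose value and which to the end-of-trial value, so that the Bowdle paragraph and SAP 6.7 agree.

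**Cost.** SAP wording and, under the main option, a longer table: 13 items x 7 change times = 91 summaries per group instead of 13 x 1 = 13. The SRD values are already scheduled, listed and plotted, so no new data are needed.

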7.6 DETERMINATION OF SAMPLE SIZE

SRD part

It is planned to include a total of up to 64 subjects in this trial. The planned sample size is not based on a power calculation. The size of 8 subjects per dose group (6 on active treatment, and 2 on placebo) is commonly used in single-rising dose studies of the present type and is in

Proprietary confidential information © 2018 Boehringer Ingelheim International GmbH or one or more of its affiliated companies

general considered as sufficient for the exploratory evaluation of single dose safety and pharmacokinetics [[R95-0013](#)].

Additional subjects may be entered to allow testing of additional doses on the basis of experience gained during the trial conduct (e.g. preliminary PK data), provided the planned and approved highest dose will not be exceeded. Thus, the actual number of subjects entered may exceed 64 but will not exceed 72 subjects entered.

BA part (food effect evaluation)

It is planned to enter a maximum of 24 subjects in this part of the trial: 12 subjects receiving 50mg and 100mg of BI 1358894. With this sample size, a certain precision in estimating the ratio of geometric means (test/reference) can be expected with 95% probability. Precision is defined through the ratio of upper to lower confidence interval limit. Note that the precision is independent of the actual ratio of geometric means.

For this first-in-man study, no information on intra-subject variability is available. Therefore, [Table 7.6: 1](#) provides an overview on the achievable precision for estimating the ratio of geometric means (test/reference) when comparing the formulations for two different gCV.

For illustrative purposes, the expected 90% confidence intervals with 95% coverage probability are displayed for different values of geometric means ratios T1/R.

Table 7.6: 1

Precision and illustrative two-sided 90% confidence intervals around selected ratios of geometric means (T1/R) for different gCVs in a two way cross-over design trial (N=12)

N	gCV	gMean Ratio [%]	CI of gMean Ratio	Precision w%
12	15%	100	(86.13, 116.11)	15%
		150	(129.19, 174.16)	
		200	(172.26, 232.21)	
	20%	100	(82.01, 121.93)	20%
		150	(123.02, 182.89)	
		200	(164.03, 243.86)	
	25%	100	(78.15, 127.95)	25%
		150	(117.23, 191.93)	
		200	(156.31, 255.91)	
	30%	100	(74.54, 134.16)	29%
		150	(111.80, 201.25)	
		200	(149.07, 268.33)	

Ratio of the geometric means (test/reference) for a PK endpoint defined by $(\exp(\mu_T)/\exp(\mu_R))$

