10.2 BOWDLE VAS-SCORE

Bowdle VAS-score (English version):

	My body or body parts seemed to change their shape or position	
Not at all	<hr/>	Extremely
	My surroundings seemed to change in size, depth, or shape	
Not at all	<hr/>	Extremely
	The passing of time was altered	
Not at all	<hr/>	Extremely
	I had feelings of unreality	
Not at all	<hr/>	Extremely
	It was difficult to control my thoughts	
Not at all	<hr/>	Extremely
	The intensity of colors changed	
Not at all	<hr/>	Extremely
	The intensity of sound changes	
Not at all	<hr/>	Extremely
	I heard voices or sounds that were not real	
Not at all	<hr/>	Extremely
	I had the idea that events, objects, or other people had particular meaning that was specific for me	
Not at all	<hr/>	Extremely
	I had suspicious ideas or the belief that others were against me	
Not at all	<hr/>	Extremely
	I felt high	
Not at all	<hr/>	Extremely
	I felt drowsy	
Not at all	<hr/>	Extremely
	I felt anxious	
Not at all	<hr/>	Extremely

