## 6. GENERAL ANALYSIS DEFINITIONS

### 6.1 TREATMENTS

It is planned that 64 healthy male subjects will enter the SRD part (8 per dose group, 6 on active and 2 on placebo) and 24 healthy males will enter the FE part (12 per dose group, all on active) of the study.

For details of dosage and formulation see Tables 6.1:1 and 6.1:2 below.

Table 6.1: 1 Labels for treatments for use in the CTR (SRD Part)

Treatment		Short label
P*	Placebo, tablet, qd	Placebo
AA	BI 1358894, 3*1 mg tablet, po, qd	BI 3mg
CA	BI 1358894, 6*1 mg tablet, po, qd	BI 6mg
AB	BI 1358894, 2*5 mg tablet, po, qd	BI 10mg
AC	BI 1358894, 1*25 mg tablet, po, qd	BI 25mg
AD	BI 1358894, 2*25 mg tablet, po, qd	BI 50mg
AE	BI 1358894, 1*100 mg tablet, po, qd	BI 100mg
AF	BI 1358894, 2*100 mg tablet, po, qd	BI 200mg
CD	BI 1358894, 2*100 mg tablet, po, qd, fed	BI 200mg fed

\*: The placebo control group in the safety evaluation will consist of all placebo treated subjects, regardless of the dose group in which they were treated.

Table 6.1: 2 Labels for treatments for use in the CTR (FE Part)

Treatment		Short label
W	BI 1358894, 2*25 mg tablet, po, qd, fed	BI 50mg fed
X	BI 1358894, 2*25 mg tablet, po, qd, fasted	BI 50mg fast
Y	BI 1358894, 1*100 mg tablet, po, qd, fed	BI 100mg fed
Z	BI 1358894, 1*100 mg tablet, po, qd, fasted	BI 100mg fast

The following separate study phases will be defined for the analyses of AEs:

- **Screening** (ranging from 0:00 h on day of informed consent until administration time of study drug)

- **On treatment**

(SRD part: separately for each treatment, ranging from the time of first administration of BI / Placebo until 0:00h on the day after trial termination date;

FE part: separately for each treatment, ranging from the time of first administration of BI until administration time of next study drug dose or 0:00h on the day after trial termination date)

Please note that all AEs reported between start of trial drug administration and the last per-protocol contact will be considered on treatment (i.e. no follow-up period is considered in this trial).

Displays of AEs will be presented separately for the treatments described in [Table 6.1: 1](#) and [Table 6.1: 2](#) above.

Two types of AE displays will be provided in the report:

**A)** Section 15.3 (separately for SRD and FE part) and Appendix 16.1.13.1.8 (for ClinicalTrials.gov and EudraCT only but combined for SRD and FE part) of the CTR displays:

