## 7. PLANNED ANALYSIS

The SRD and FE part will be evaluated separately.

The placebo group in the safety evaluation of the SRD part will consist of all placebo treated subjects, regardless of the dose group in which they were treated.

Safety analysis (refer to [Section 7.8](#)) will be performed by and will be presented in Sections 15.1 to 15.4 of the CTR and in Appendix 16.2 and 16.1.13.1.

Inferential statistical analyses of PK endpoints (refer to [Section 7.5.2](#)) will also be performed by and will be presented in Section 15.5 of the CTR and in Appendix 16.1.13.3.

Descriptive data analysis of PK parameters and concentrations will be performed by the department of Translational Medicine and Clinical Pharmacology at BI and will be presented in Section 15.6 of the CTR.

The format of the listings and tables will follow the standards defined in the BI corporate guideline “Reporting of Clinical Trials and Project Summaries” [001-MCG-159] ([6](#)) with the exception of those generated for PK-calculations.

In the SRD part, the individual values of all subjects will be listed, sorted by treatment group, subject number, and visit.

In the FE part, the individual values of all subjects will be listed, sorted by treatment sequence, subject number, visit and actual treatment (if appropriate).

The listings will be included in Appendix 16.2 of the CTR.

For end-of-text tables, the set of summary statistics for non-PK parameters is:

N	number non-missing observations
Mean	arithmetic mean
SD	standard deviation
Min	minimum
Median	median
Max	maximum

For analyte concentrations, the following descriptive statistics will additionally be calculated:

CV	arithmetic coefficient of variation
gMean	geometric mean
gCV	geometric coefficient of variation

For PK parameters, the following descriptive statistics will additionally be calculated:

CV	arithmetic coefficient of variation
gMean	geometric mean
gCV	geometric coefficient of variation
P10	10th percentile

Q1	1st quartile
Q3	3rd quartile
P90	90th percentile

The data format for descriptive statistics of concentrations will be identical with the data format of the respective concentrations. The descriptive statistics of PK parameters will be calculated using the individual values with the number of decimal places as provided by the evaluation program. Then the individual values as well as the descriptive statistics will be reported with three significant digits in the CTR.

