#### Visual analogue scale – Bond and Lader

For Bond and Lader VAS, three factors will be calculated using the loadings (regression weights) from the factor analysis in (12), which are shown in Table [7.8.5.3:1](#) below. The individual scores on each scale will be multiplied by the scale's factor loading and totaled within the three factors. The summed scores will then be divided by the sum of loadings for each factor.

$$\text{Alertness} = F_1 = 1 / \sum w_{1i} * \sum (w_{1i} * VAS_i)$$

$$\text{Contentment} = F_2 = 1 / \sum w_{2i} * \sum (w_{2i} * VAS_i)$$

$$\text{Calmness} = F_3 = 1 / \sum w_{3i} * \sum (w_{3i} * VAS_i)$$

where

$VAS_i$  measured scale i; where  $i = 1, \dots, 16$

$w_{fi}$  factor loading for factor f and scale i; where  $f = 1, 2, 3$  and  $i = 1, \dots, 16$ ,

Since some scales for these loadings are reversed compared to the scales in the questionnaire the corresponding individual scores have to be reversed (100 – measured score value (mm)) before multiplication. Descriptive statistics of the three factors over time and for the difference from baseline will be provided. Furthermore, for the SRD part, the change from

baseline of the three factors will be presented graphically over time (arithmetic means + standard deviation).

Table 7.8.5.3: 1 Factor loadings for Bond and Lader VAS

Measured score value		Factor loadings to		
		Alertness	Contentment	Calmness
Alert / Drowsy	1. Alert	0.827	0.088	0.008
Calm / Excited	2. Calm	0.049	0.029	0.845
Strong / Feeble	3. Strong	0.618	0.142	0.328
Muzzy / Clear-headed *	4. Clear-headed	0.755	0.149	0.080
Well-coordinated / Clumsy	5. Well-coordinated	0.642	0.122	0.424
Lethargic / Energetic *	6. Energetic	0.776	0.174	-0.019
Contented / Discontented	7. Contented	0.233	0.677	0.278
Troubled / Tranquil *	8. Tranquil	0.133	0.697	0.429
Mentally slow / Quick-witted *	9. Quick-witted	0.635	0.340	-0.138
Tense / Relaxed *	10. Relaxed	0.031	0.445	0.677
Attentive / Dreamy	11. Attentive	0.792	0.179	0.098
Incompetent / Proficient *	12. Proficient	0.593	0.328	0.027
Happy / Sad	13. Happy	0.270	0.823	0.051
Antagonistic / Amicable *	14. Amicable	0.159	0.738	0.172
Interested / Bored	15. Interested	0.614	0.412	-0.006
Withdrawn / Gregarious *	16. Gregarious	0.343	0.594	-0.217

\* Measured score value will be reversed

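### No per-subject post-dose peak is planned for the Bowdle scale, so summaries by time point cannot show how many of six subjects reacted when reactions come at different times

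*SAP*

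**What the plan says.** Protocol 5.2.5.3 makes the two visual analogue scales a safety instrument: "Possible psychedelic effects will be monitored and evaluated as safety measurement". Every line is 100 mm long and is scored in mm from its left end. The thirteen Bowdle items (Protocol 10.2), of which the first reads "My body or body parts seemed to change their shape or position", run from absence of the sensation to its extreme.

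SAP 7.8.5.3 speaks in three places:

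- **Opening text.** The SRD part has post-dose assessments at 2, 4, 8, 24, 34 and 48 h. Baseline is the last value before dosing. Both scales are to be listed and summarised descriptively over time.
- **Bowdle paragraph.** The items are tabulated at screening and at the final examination, with screening as baseline. The remaining assessments go to listings. For the SRD part, "the change from baseline of the individual scales will be presented graphically over time (arithmetic means + standard deviation".
- **Bond and Lader paragraph.** The three factors get statistics over time and a similar graph: the change from "baseline of the three factors will be presented graphically over time (arithmetic means + standard deviation".

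Neither scale gets a per-subject peak or a count of subjects who reacted. The default statistics in SAP 7 for non-PK tables are N, mean, SD, min, median and max.

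On numbers, SAP 6.1 states: "It is planned that 64 healthy male subjects will enter the SRD part (8 per dose group, 6 on active and 2 on placebo". Placebo is pooled (SAP 7): "The placebo group in the safety evaluation of the SRD part will consist of all placebo treated subjects". Protocol 7.6 adds: "The planned sample size is not based on a power calculation".

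**The concern.** A psychedelic effect of a new CNS drug may show in only a few of six subjects, and not necessarily at the same hour. The reader of the report then wants to know how many subjects at this dose reacted, how strongly, and how that compares with placebo. A mean + SD at each nominal time does not answer the first question. It treats the six values at each time as a fresh sample and drops the link between a subject's values over time.

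A full table by time point would drop the same link. The gap is therefore separate from the conflict inside SAP 7.8.5.3 over whether post-dose Bowdle scores are tabulated at all. At stake is whether one subject with a lasting reaction can be told from several subjects with brief ones when dose levels are compared.

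**Working it through.** **Inputs from the documents**

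- Group size: 6 active subjects per dose. Check of the SAP 6.1 total: 8 groups × (6 + 2) = 64, of whom 8 × 6 = 48 are active and 8 × 2 = 16 are pooled placebo.
- Post-dose times: six (SAP 7.8.5.3). Scale: 0 to 100 mm (Protocol 5.2.5.3).

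**Assumptions.** The documents give no Bowdle data. A reaction is set at M = +60 mm for illustration, all other changes are 0, and predose scores are near 0.

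**Formulas.** If k of n = 6 subjects react at a given time:

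- mean = M·k/n
- SD = M·√[k(n − k)/(n(n − 1))]

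| k at one time | mean | SD | mean + SD |
|---|---|---|---|
| 1 | 60 × 1/6 = 10.0 | 60 × √(5/30) = 24.5 | 34.5 |
| 2 | 60 × 2/6 = 20.0 | 60 × √(8/30) = 31.0 | 51.0 |
| 3 | 60 × 3/6 = 30.0 | 60 × √(9/30) = 32.9 | 62.9 |

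**Two scenarios with the same summary**

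- A: one subject is at +60 at 2, 4 and 8 h.
- B: three different subjects are at +60, one at 2 h, one at 4 h and one at 8 h.

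At each of these three times, both scenarios hold one value of 60 and five of 0. Hence N 6, mean 10, SD 24.5, min 0, median 0, max 60 in both, and zeros at 24, 34 and 48 h. The curves are identical, and so is a full table by time point with the SAP's default statistics. The equality holds for any M.

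**Per-subject peaks in the same scenarios**

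- A: 60, 0, 0, 0, 0, 0. Mean 10.0, SD 24.5, median 0, max 60.
- B: 60, 60, 60, 0, 0, 0. Mean 30.0, SD 32.9, median 30, max 60.

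The peaks separate the scenarios.

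**With background noise.** In 20,000 simulated groups per noise level, predose and post-dose scores carried noise |N(0, s)|, and one subject reacted at one time. The share of groups whose highest value exceeded the 95th percentile of noise-only groups was:

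| s, M (mm) | mean line | mean + SD | largest individual change |
|---|---|---|---|
| 5, 30 | 0.70 | 1.00 | 1.00 |
| 10, 60 | 0.69 | 1.00 | 1.00 |
| 10, 30 | 0.20 | 0.51 | 0.65 |

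The mean line dilutes a single reaction, but the SD bar recovers most of the signal. What it does not recover is the number of reactors. With s = 10 and M = 60, the median height of the curve's peak is 10.0 mm for one reactor and 12.1 mm for three staggered ones. The mean of the individual peaks (median over runs) is 17.2 against 34.3 mm.

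**The case against.** A reader might infer that the planned curves hide a psychedelic reaction. The documents do not support that. The SD is part of the graph and is 2.45 times the mean when one subject reacts (24.5/10). Three simultaneous reactors give a mean of 30 mm.

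A reader might also infer that two or three reactors will usually look like one. If each reactor peaks once, at a uniformly random one of the six times, no two peaks coincide with probability 5/6 for two reactors and 5/9 for three. But each such reactor then adds its own bump, so the curves still differ. The fractions also rest on the uniform timing. With peaks confined to 2, 4 and 8 h they fall to 2/3 and 2/9, and at 2 and 4 h only to 1/2 and 0. Protocol 2.3.2.3 expects the period of peak effect within about a day of dosing. True ambiguity needs reactions of different length, as in scenarios A and B.

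Other routes exist. Individual values are listed. The final examination is also post-dose and is tabulated. The opening text of SAP 7.8.5.3 would add a maximum at each time, which shows strength. The synopsis names clinically relevant Bowdle findings among the adverse events, and SAP 7.8.1 counts subjects with events.

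These points limit the concern but do not remove it. A listing holds 6 × 6 = 36 post-dose values per item and active dose and gives no dose-level comparison with placebo. The adverse event route depends on the judgement of an investigator who knows the treatment (Protocol 4.1.5.2), and no score rule is set. A maximum by time is the same in A and B.

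The argument from a floor at 0 applies to the Bowdle items. It does not carry over to the bipolar Bond and Lader scales, whose factors already get statistics over time.

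**Conclusion.** The point holds as a minor, worthwhile improvement. Neither scale has a per-subject post-dose peak. On the Bowdle paragraph's own text, scores from 2 to 48 h are aggregated only as mean + SD curves, which conflicts with the opening text of the same section. Either way, summaries by time point can be identical for 1/6 and 3/6 reactors, and this is exact arithmetic. How often it would matter depends on reactions differing in time and length and on predose scores near zero, which the documents neither state nor exclude. The trial is descriptive, so no test or sample size is affected. The food effect part is not affected either, because the SAP schedules no acute post-dose VAS there.

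**What to change.** In SAP 7.8.5.3, for the SRD part:

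1. Reconcile the opening text with the Bowdle paragraph, both on whether post-dose statistics over time are tabulated and on which baseline applies (last predose value or screening).
2. For each Bowdle item, derive each subject's largest change from the last predose value over 2 to 48 h.
3. Plot these individual peaks by dose group and pooled placebo.
4. Tabulate them with the full default set (N, mean, SD, min, median, max). Median, min and max alone would not do: one and two reactors of six both give 0, 0 and 60, while the means are 10 and 20.
5. Keep the mean curves as supportive.

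No cut-off is needed. A similar summary for the Bond and Lader factors, in both directions, is optional.

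The cost is SAP wording plus one table and one figure set covering 13 items, from data already collected. The downside is that a maximum over six times is biased upward by noise. In the simulation with s = 10 and M = 60, one reactor gave a typical mean peak of 17.2 mm instead of 10. The peaks must therefore be read against the same maximum in the 16 planned placebo subjects.
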